#### 5.1.2.1. Carfilzomib Safety Considerations

Based on previous Phase I and II carfilzomib studies, the following observations have been noted:

- A “first dose effect” has been seen, which is notable for fever, chills, rigors, and/or dyspnea occurring during the evening following the first day of infusion and an

increase in creatinine on Day 2, which may be the clinical sequelae of rapid tumor lysis and/or cytokine release.

- Should a “first dose” effect occur at any point during Cycle 1 or 2, treatment with high dose glucocorticoids (e.g. methylprednisolone 50–100 mg) is recommended. In addition, intravenous fluids, vasopressors, oxygen, bronchodilators, and acetaminophen should be available for immediate use and instituted, as medically indicated.
- Dexamethasone 4 mg PO/IV will be administered prior to all carfilzomib doses during the first cycle and prior to all carfilzomib doses during the first dose-escalation (for example from 20 mg/m^2 to 27 mg/m^2) cycle. If treatment-related fever, rigors, chills, and/or dyspnea are observed post any dose of carfilzomib after dexamethasone has been discontinued, dexamethasone (4 mg PO/IV) should be re-started and administered prior to subsequent doses.
- Patients should receive acyclovir or similar (famciclovir, valacyclovir) anti-varicella (anti-herpes) agent prophylaxis. In addition, patients may receive antibiotic prophylaxis with ciprofloxacin or other fluoroquinolone (or timethoprim/sulfamethoxazole if fluoroquinolones are contradicted) if clinically indicated.
- CrCl changes are mostly transient, reversible, and non-cumulative. All patients should be well hydrated. Clinically significant electrolyte abnormalities should be corrected prior to dosing with carfilzomib. Renal function must be monitored closely during treatment with carfilzomib. Serum chemistry values, including creatinine, are strongly encouraged prior to each dose of carfilzomib during Cycles 1 and 2. The decision will be at the discretion of the treating physician. Carfilzomib must be held for subjects with a CrCl < 15 mL/min at any time during study participation.

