Recently in the PX-171-007 trial, patients have been treated with carfilzomib given as a 30-minute infusion in order to minimize  $C_{max}$ -related infusion events. The PX-171-007 trial was amended and doses of 20/36 (20 mg/m^2 given on Days 1 and 2 of cycle 1 only; followed by 36 mg/m^2 for all subsequent doses), 20/45, 20/56 mg/m^2 and so forth are being investigated. Doses of 20/56 mg/m^2 are currently being given in two separate cohorts of patients with advanced MM and advanced solid tumors; the lower doses were well tolerated. Preliminary tolerability information at this dose level (20/56 mg/m^2) indicated that it is reasonably well tolerated, with minimal infusion reactions. In some cases at 20/56mg/m^2, dexamethasone was increased from 4mg/dose to 8mg with the 56mg/m^2 doses in order to reduce fevers and hypotension. As of March 20, 2010, seven patients have received 20/56mg/m^2 with tolerability. Patients with advanced, refractory MM being treated at 36mg/m^2 and 45mg/m^2 have shown very good tolerability (>6 months in some cases) with documented minimal and partial responses in these heavily pretreated patients. These data indicate that carfilzomib 30-minute infusion can be given at very high levels, with >95% inhibition of blood proteasome levels achievable and with (at least) acute tolerability. As a result, carfilzomib is now administered as a 30-minute infusion if the dose is  $\geq 36$ mg/m^2.

In addition to the above observations, a phase I study of carfilzomib in patients with relapsed and refractory multiple myeloma was reported in abstract form at the 2009 American Society of Hematology meeting which demonstrated that carfilzomib can be safely administered to patients with substantial renal impairment (CrCl < 30, including patients on dialysis) without dose adjustment (Badros et al. 2009). These data indicate that carfilzomib does not exacerbate underlying renal dysfunction, and confirm the “pre-renal” etiology of the BUN/creatinine elevations observed with IV bolus carfilzomib.

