## 3. PATIENT ELIGIBILITY AND WITHDRAWAL CRITERIA

### 3.1. Inclusion Criteria

1. Eligible participants must have multiple myeloma using standard criteria (Appendix B).
2. Patients must have measurable disease requiring systemic therapy defined as at least one of the following:
  - Serum M-protein  $\geq 0.5$  g/dl ( $\geq 5$  g/l)
  - Urine M-protein  $\geq 200$  mg/24 hrs
  - Serum free light chain assay: involved free light chain level  $\geq 10$  mg/dl ( $\geq 100$  mg/l) provided the serum free light chain ratio is abnormal
3. Must have progressed during or after at least one previous bortezomib-containing treatment regimen. Patients who have received previous high-dose therapy/autologous stem cell transplantation are eligible.
4. Eastern Cooperative Oncology Group (ECOG) performance status of 0-2. (see Appendix A).
5. Must meet the following laboratory criteria:
  - Absolute neutrophil count (ANC)  $\geq 1000/\mu\text{L}$ ;
  - Platelets  $\geq 70,000/\mu\text{L}$ ;
  - AST or ALT and alkaline phosphatase (ALP) must be  $\leq 2.5$  x ULN, or  $\leq 5$  x ULN in patients with plasmacytomas of the liver;
  - Total bilirubin  $\leq 1.5$  x the institutional ULN;
  - Serum creatinine  $\leq 1.5$  x ULN or calculated creatinine clearance  $\geq 50$  ml/min;
  - Serum potassium, calcium, magnesium WNL (These may be corrected prior to starting therapy, to make the patient eligible.)
6. Ability to swallow oral medications.
7. Baseline MUGA or ECHO must demonstrate left ventricular ejection fraction (LVEF)  $\geq$  the lower limit of the institutional limits of normal.

8. Male or females  $\geq 18$  years of age.
9. Female patients must not be of childbearing potential or must agree to use adequate contraceptive measures.
10. Male patients willing to use adequate contraceptive measures.
11. Willingness and ability to comply with the trial and follow-up procedures.
12. Ability to understand the nature of this trial and give written informed consent.

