### **6.3. Carfilzomib Dose Modifications for Non-Hematologic Toxicities**

Treatment with carfilzomib and panobinostat should be held for  $\geq$  grade 3 events until resolved to  $\leq$  grade 1 or return to baseline. If the adverse event was not treatment-related, or was attributable to panobinostat, subsequent treatment with carfilzomib may be resumed at full dose after resolution to  $\leq$  grade 1 or return to baseline.

If the event was carfilzomib-related, subsequent treatment with carfilzomib will resume at one level dose reduction (see Table 3). If toxicity continues or recurs, a 2nd carfilzomib dose reduction is permitted unless the patient is already receiving the lowest dose level shown in Table 3. If toxicity continues, the patient should be discontinued from treatment.

If there is no resolution of carfilzomib-related toxicity after 2 weeks of withholding carfilzomib (up to 3 weeks for infection treatment), carfilzomib will be discontinued.

Specific carfilzomib-associated non-hematologic toxicities are addressed in Table 7.

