**Table 8. Carfilzomib Dose Modifications for Non-Hematologic Toxicity**

Event	Action to be Taken
Allergic reaction/hypersensitivity Grade 2 – 3 Grade 4	Hold until ≤ Grade 1, reinstitute at full dose. Discontinue
Tumor lysis syndrome  (≥ 3 of following: ≥ 50% increase in creatinine, uric acid, or phosphate; ≥ 30% increase in potassium; ≥ 20% decrease in calcium; or ≥ 2-fold increase in LDH)	Hold carfilzomib until all abnormalities in serum chemistries have resolved. Reinstitute at full doses.
Infection Grade 3 or 4	Hold carfilzomib (no more than 3 weeks) until systemic treatment for infection complete. If no neutropenia, restart at full dose. If neutropenic, follow neutropenic instructions (Table 4).
Herpes zoster or simplex of any grade	Hold carfilzomib until lesions are dry. Reinstitute at full dose.
Neuropathy Grade 2 treatment emergent neuropathy with pain or Grade 3 neuropathy  Grade 4 neuropathy	Continue to dose. If neuropathy persists for more than two weeks hold carfilzomib until resolved to ≤ Grade 2 without pain. Then restart at 1 dose decrement  Discontinue carfilzomib
Renal Dysfunction  CrCl ≤ 30 mL/min	Hold until CrCl > 30 mL/minute; restart at 1 dose decrement
Congestive heart failure	Any subject with symptomatic congestive heart failure, whether or not drug related, must have the dose held until resolution or return to baseline, after which treatment may continue at a reduced dose, or the subject may be withdrawn from the study. If no resolution after 2 weeks, the subject will be withdrawn from the study.
Hypertension	All patients should be evaluated for hypertension and treated as needed. If hypertension cannot be controlled, reduce carfilzomib.

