#### **6.4.3. Acute Renal Disorder**

Cases of acute renal failure have been reported in subjects who received carfilzomib. Acute renal failure was reported more frequently in subjects with advanced relapsed and refractory multiple myeloma who received carfilzomib monotherapy. This risk was increased in subjects with a decrease in estimated creatinine clearance, calculated using Cockcroft and Gault equation, prior to receiving carfilzomib. Monitor renal function with regular measurement of the serum creatinine and/or estimated creatinine clearance. Reduce or withhold dose as appropriate.

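### Section 5.1.2.1 and Table 8 set different creatinine clearance thresholds for holding carfilzomib (below 15 against 30 mL/min or below), and nothing in the protocol reconciles them

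*Combined protocol and SAP*

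**What the plan says.** Three places in the current protocol text tell a site what to do with carfilzomib when renal function falls.

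- Section 5.1.2.1 (Carfilzomib Safety Considerations): "Carfilzomib must be held for subjects with a CrCl < 15 mL/min at any time during study participation". The section gives no clearance at which dosing may resume and says nothing about the dose on resumption.
- Table 8 in Section 6.3 (Renal Dysfunction row): the trigger is "CrCl ≤ 30 mL/min" and the action is "Hold until CrCl > 30 mL/minute; restart at 1 dose decrement".
- Section 6.4.3 (Acute Renal Disorder): renal function is to be monitored, followed by "Reduce or withhold dose as appropriate". No clearance value is given.

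Three further statements bear on which of these a site would use. The opening of Section 6 says that criteria for interrupting and resuming treatment for toxicity are in the tables that follow. Section 8.2.6 places management of carfilzomib toxicities in Sections 6.3 and 6.4 and the Investigator's Brochure. The text of Section 6.3 sends the reader to Table 7 for specific carfilzomib non-hematologic toxicities, but Table 7 is the panobinostat QTcF table and the carfilzomib table is Table 8.

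**The concern.** Section 5.1.2.1 and Table 8 concern the same drug, the same measurement and the same action, yet they set different thresholds. Neither refers to the other. The 15 mL/min sentence is mandatory and applies throughout participation, so it cannot be read as limited to screening or to Cycle 1.

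A site that works from 5.1.2.1 would find no hold required for a patient at, say, 20 mL/min. A site that works from Table 8 would stop the drug and later resume it one level lower. Section 6.4.3 links carfilzomib to acute renal failure, with risk increased when clearance is reduced, so the hold rule is a safety rule and not a formality. If sites read it differently, carfilzomib exposure and the counts of holds and dose reductions would depend partly on which section was consulted.

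**Working it through.** No sample size, power or error rate depends on this point, so there is no statistical figure to reproduce. The check sets the two rules side by side, looks for text that would reconcile them, and asks whether the affected range can be reached.

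**Step 1. The two rules by CrCl (mL/min).**

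| CrCl | Section 5.1.2.1 | Table 8, renal row |
|---|---|---|
| 5 | hold | hold; restart above 30, one level lower |
| 14.9 | hold | same |
| 15 | no hold stated | same |
| 20 | no hold stated | same |
| 30 | no hold stated | same |
| 30.1 | no hold stated | no hold |
| 50 | no hold stated | no hold |

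The rules differ for 15 ≤ CrCl ≤ 30. The ratio of the thresholds is 30/15 = 2. Below 15 both require a hold, but only Table 8 says how it ends. Every patient below 15 is also at or below 30, so the rules are nested and no patient exists for whom obeying Table 8 breaches 5.1.2.1.

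**Step 2. Is there reconciling text?**

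- The opening of Section 6 and Section 8.2.6 favor Section 6 as the place for toxicity rules. Neither mentions the 15 mL/min sentence or says that it is superseded.
- Section 6.3, which should lead to the 30 mL/min rule, names the wrong table.
- Section 6.4.3 lies within the part of Section 6 that these statements point to, and it leaves the decision to judgment without a threshold.
- On dose after restart, the text of 6.3 says that, for events not related to treatment or attributed to panobinostat, "subsequent treatment with carfilzomib may be resumed at full dose after resolution". The renal row of Table 8 reduces the dose without mentioning attribution, although another row of the same table (other non-hematologic toxicity) is limited to carfilzomib-related events.
- The background does not settle the intent either. Section 1.3.1.1 cites a phase I study as showing safe administration in substantial renal impairment ("CrCl < 30, including patients on dialysis) without dose adjustment").

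**Step 3. Can a patient be in the range?** Section 3.1 accepts serum creatinine up to 1.5 "x ULN or calculated creatinine clearance" of at least 50 mL/min, so a clearance of 50 is not required of everyone. The illustration below uses assumed values that are not in the documents: age, weight, an upper limit of normal (ULN) for creatinine of 1.0 to 1.3 mg/dL, and the standard Cockcroft-Gault form, CrCl = (140 − age) × weight / (72 × creatinine), times 0.85 for women. Creatinine is set at the eligibility limit, 1.5 × ULN, which is 1.5 to 1.95 mg/dL.

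- Woman, 80 years, 55 kg: 60 × 55 / (72 × 1.5) × 0.85 = 26.0; with creatinine 1.95, 20.0.
- Man, 65 years, 80 kg: 75 × 80 / (72 × 1.5) = 55.6; with creatinine 1.95, 42.7.

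So some patients could meet the creatinine limb while already in the range, and others would be well above it. This shows that the range can be reached. It does not estimate how often.

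**The case against.** The best defense is that the protocol assigns toxicity holds to Section 6, that 5.1.2.1 is introduced as observations from earlier carfilzomib studies, and that the 15 mL/min sentence is a leftover: the amendment history lists it under Section 6.4 and later records the safety guidelines moving to 5.1.2. The wrong table number in 6.3 looks like a renumbering slip that a careful reader would see through. On that reading Table 8 governs and the 15 mL/min line is merely redundant.

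Much of this stands. It narrows the ambiguity and makes Table 8 the more natural place to look. It does not remove the ambiguity, because the sentence in 5.1.2.1 is worded as an obligation, remains in the current text, and is not subordinated to Table 8 anywhere.

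The defense also rightly blocks several stronger readings that a reader might draw.

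- *That the two sections give opposite instructions at 15 to 30 mL/min.* They do not. Section 5.1.2.1 is silent on that range and does not direct sites to dose.
- *That the restart rules conflict, for example that recovery from below 15 to 20 mL/min ends the hold under 5.1.2.1.* That section contains no restart rule, so this is an inference from where its hold begins.
- *That dose-escalation decisions were affected.* In Cycle 1, two of six carfilzomib doses held would leave 4/6 = 67%, below the 75% in the dose-limiting toxicity definition. However, that item refers to both agents, Section 5 reports no dose-limiting toxicities in the Phase I portion, and no document shows a renal hold altering a cohort decision.
- *That many patients are exposed.* No count is given. Section 5.1.2 also excludes patients whose renal impairment contraindicates the hydration program.

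**Conclusion.** The point holds as an internal inconsistency in a safety rule. The two carfilzomib hold thresholds differ by a factor of two. From 15 to 30 mL/min inclusive, Table 8 requires a hold and a one-level reduction at restart, while 5.1.2.1 requires nothing. Following Table 8 satisfies both, so the practical risk is confined to a site that relies on 5.1.2.1, or on the discretionary wording of 6.4.3, without reaching Table 8. The wrong table reference in 6.3 makes that easier.

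The conclusion rests on the protocol text alone. The clearance illustration supports only the statement that the range can be reached, and it depends on assumed patient values. The number of patients affected is unknown, and no endpoint definition, sample size or planned analysis changes. The inconsistency should be corrected because a threshold for stopping a drug for renal toxicity ought to read the same wherever a site looks. No view is taken on which threshold or restart dose is clinically right.

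**What to change.** Reconcile Section 5.1.2.1, the text of Section 6.3, the renal row of Table 8 and Section 6.4.3 so that the protocol states:

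1. one CrCl threshold for holding carfilzomib;
2. one CrCl threshold for restarting it;
3. one statement on the dose after restart, including whether attribution of the event matters.

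State these in one place and have the other sections refer to it. Correct the reference in Section 6.3 from Table 7 to Table 8. The values are for the sponsor and investigators to decide on clinical grounds.

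The cost is wording, carried through the amendment process in Section 13.1. No assessment, sample size or analysis needs to change.

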### 5.1.3. Window for Holidays and Vacations

For holidays and vacations it is preferred to plan ahead and adjust D1 of treatment +/- 48 hours of the cycle the patient plans to be gone for treatment, so that the patient follows the treatment schedule per protocol. If it is not possible to adjust D1, the carfilzomib infusion days may be adjusted +/- 48 hours after cycle 1 for a holiday or vacation. There is no window allowed during cycle 1 and for the panobinostat doses except for D1 with the window described above.

### 5.2. Phase I

The Phase I doses to be tested are defined in Table 2.

**Table 2. Phase I Dose Levels**

28-Day Cycles	Cycle 1	Cycle 2 to Progression
Dose Level -1		

Carfilzomib	15 mg/m  IV D1, 2 / 20 mg/m  IV D8, 9, 15, 16	20 mg/m  IV D 1, 2, 8, 9, 15, 16
Panobinostat	20 mg D 1, 3, 5, 15, 17, 19	20 mg D 1, 3, 5, 15, 17, 19
Dose Level 1		
Carfilzomib	20 mg/m  IV D1, 2 / 27 mg/m  IV D8, 9, 15, 16	27 mg/m  IV D 1, 2, 8, 9, 15, 16
Panobinostat	20 mg D 1, 3, 5, 15, 17, 19	20 mg D 1, 3, 5, 15, 17, 19
Dose Level 2		
Carfilzomib	20 mg/m  IV D1, 2 / 36 mg/m  IV D8, 9, 15, 16	36 mg/m  IV D 1, 2, 8, 9, 15, 16
Panobinostat	20 mg D 1, 3, 5, 15, 17, 19	20 mg D 1, 3, 5, 15, 17, 19
Dose Level 3		
Carfilzomib	20 mg/m  IV D 1, 2 / 45 mg/m  IV D8, 9, 15, 16	45 mg/m  IV D 1, 2, 8, 9, 15, 16
Panobinostat	20 mg D 1, 3, 5, 15, 17, 19	20 mg D 1, 3, 5, 15, 17, 19
Dose Level 4		
Carfilzomib	20 mg/m  IV D 1, 2 / 45 mg/m  IV D8, 9, 15, 16	45 mg/m  IV D 1, 2, 8, 9, 15, 16
Panobinostat	30 mg D 1, 3, 5, 15, 17, 19	30 mg D 1, 3, 5, 15, 17, 19

**Table 3. Parallel Dose Escalation Study – Dose Levels 5 and 6**

28-Day Cycles	Cycle 1	Cycle 2 to Progression
Dose Level 5		
Carfilzomib	20 mg/m  IV D 1, 2 / 56 mg/m  IV D 8, 9, 15, 16	56 mg/m  IV D 1, 2, 8, 9, 15, 16
Panobinostat	30 mg D 1, 3, 5, 15, 17, 19	30 mg D 1, 3, 5, 15, 17, 19
Dose Level 6		
Carfilzomib	20 mg/m  IV D 1, 2 / 56 mg/m  IV D 8, 9, 15, 16	56 mg/m  IV D 1, 2, 8, 9, 15, 16
Panobinostat	20 mg D 1, 3, 5, 15, 17, 19	20 mg D 1, 3, 5, 15, 17, 19

A parallel Phase I study will occur to evaluate a minimum of 3 patients and a maximum of 6 patients following a standard dose escalation design at additional dose levels of the combination of carfilzomib and panobinostat.

Patients will enter in the dose level confirmed in their enrollment confirmation from SCRI Innovations.

### 5.2.1. Dose Escalation Phase I

The study will follow a standard dose-escalation design (see Table 2). For each cohort, the decision whether to dose-escalate will be made once all subjects have been

enrolled into the cohort and have received one full cycle (28 days) of study drug treatment. The following dose-escalation rules will be used:

- Initially, 3 subjects will be entered into a dose level.
- If 2 or more of the initial subjects experience dose-limiting toxicity (DLT) (see Section 5.2.2), then the MTD (see Section 5.2.3) has been exceeded.
- If none of the 3 subjects initially enrolled into this dose level cohort experiences DLT, then subsequent subjects will be enrolled in the next higher dose level.
- If 1 of the initial subjects experiences DLT, then 3 additional subjects (to a total of 6 subjects) will be enrolled in the dose level.
- If it is found that 1 of the 6 subjects in the dose level encounters DLT, then subsequent subjects will be enrolled into the next higher dose level cohort.
- If it is found that 2 or more of the 6 subjects in a dose level encounter DLT, then the MTD has been exceeded. If  $\geq 2$  of 6 patients have DLT on the first dose level tested (Dose Level 1, Table 2), dose level -1 will be evaluated. If dose level -1 is too toxic ( $\geq 2$  of 6 patients with DLT), the study will continue only after discussion by the study chair and the sponsors.

No intra-patient dose escalation is permitted.

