## 5. STUDY DESIGN

This is an open-label, non-randomized Phase I/II study of patients with relapsed or refractory multiple myeloma.

The Phase I study will determine the MTD of the combination of carfilzomib and panobinostat. The Phase I portion will follow a standard dose escalation design, beginning with dose level 1 (see Table 2). Patients will be assessed for dose-limiting toxicity (DLT) at each visit during Cycle 1 prior to receiving treatment. Dose modifications will not be permitted during Cycle 1 unless a patient experiences a DLT (see Section 5.2.2.). Treatment cycles will be administered at 28-day intervals. Panobinostat will be administered orally three times weekly during weeks 1 and 3 of each cycle (Days 1, 3, 5, 15, 17, 19). Carfilzomib will be administered intravenously on Days 1, 2, 8, 9, 15, and 16 of each cycle. During Cycle 1, the carfilzomib dose will be escalated after the Day 2 dose, if well tolerated.

A maximum of four dose levels were evaluated. No DLTs were seen during the Phase I portion.

In the Phase II portion of this study, patients with relapsed/refractory multiple myeloma will receive treatment with the dose level 4 panobinostat and carfilzomib combination. Patients will be reevaluated for response to treatment after each cycle (4 weeks). Patients with objective response or stable disease will continue treatment, with subsequent reevaluations every 4 weeks, until disease progression or unacceptable toxicity occurs.

[figure not shown]
A parallel Phase I study will occur to evaluate a minimum of 3 patients and a maximum of 6 patients following a standard dose escalation design at additional dose levels of the combination of carfilzomib and panobinostat (see Table 3).

If additional dose levels are found to be tolerable, then additional patients will be recruited into an expansion cohort which will be open at all sites - a maximum total of 36 patients (including the ones recruited into the parallel Phase I study) will be treated at this dose level. Sites will be notified about the expansion cohort and patients will enter in the dose level confirmed in their enrollment confirmation from SCRI Innovations.

Up to 80 eligible patients will be treated in the Phase I/II study. The treatment schema for the study is shown in Figure 2.

Figure 2

Treatment Schema

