#### **When the MTD has been exceeded:**

When the MTD has been exceeded, the next lower dose previously studied will be evaluated for the MTD criteria. If only 3 subjects have been treated at this dose level, 3 additional subjects will be entered into this dose level until 6 subjects total have been treated.

- Once 6 subjects have been enrolled and evaluated at this dose level, if there was  $\leq 1$  DLT, this dose level will be declared the MTD.
- If  $>1$  DLT occurred, then the MTD has been exceeded, and the next lower dose level will be similarly evaluated.
- Dose level -1 will only be tested if dose level 1 exceeds MTD.

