### **5.2.3. Definition of Maximum Tolerated Dose (MTD)**

The MTD of carfilzomib and panobinostat when given as a combination therapy will be defined as the highest dose level at which  $\leq 1$  of 6 subjects experiences dose-limiting toxicity (DLT).

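### Does the numbering of Dose Levels 5 and 6 leave the parallel Phase I without a usable escalation and expansion rule?

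*Combined protocol and SAP*

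**What the plan says.** **Rules.** Section 5.2.1 refers to Table 2, which covers Levels -1 to 4. After no DLT in three subjects, "then subsequent subjects will be enrolled in the next higher dose level"; one DLT in six has the same effect. Once the MTD has been exceeded, "the next lower dose previously studied will be evaluated for the MTD criteria". Under Section 5.2.3 the MTD "will be defined as the highest dose level at which" no more than one of six subjects has a DLT.

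**Doses.** Table 2 gives Level 4 as carfilzomib 20/45 mg/m² with panobinostat "30 mg D 1, 3, 5, 15, 17, 19". Table 3 gives Level 5 as carfilzomib 20/56 mg/m² with the same 30 mg of panobinostat, and Level 6 as carfilzomib 20/56 mg/m² with panobinostat "20 mg D 1, 3, 5, 15, 17, 19".

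**Parallel part.** The text under Table 3 provides for three to six patients "following a standard dose escalation design at additional dose levels of the combination of carfilzomib and panobinostat". It adds: "Patients will enter in the dose level confirmed in their enrollment confirmation from SCRI Innovations".

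**Expansion.** Section 5 states: "If additional dose levels are found to be tolerable, then additional patients will be recruited into an expansion cohort". It sets a ceiling of 36 at the expanded level, counting that level's Phase I patients. Section 5.3 provides one added cohort of 30, making 60 Phase II patients with the 30 at Level 4, within an overall limit of 80. Sections 10.1 and 10.4 evaluate response at two levels separately, and Section 10.4 rules out a formal comparison between them.

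**The concern.** An escalation design needs an order, and Table 3 appears to break it. If levels are followed by number, clearing Level 5 moves patients up to a smaller combination. Exceeding Level 6 moves them down to a larger one. If both are cleared, the MTD label falls on the smaller of the two.

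If levels are followed by dose, those oddities go, but two gaps stay open. When Level 5 is exceeded, the step-back rule returns to a level already studied, so nothing written opens Level 6. And Section 5 starts from several tolerable levels but ends with one cohort at one level, without saying how that level is picked. The combination given to up to 36 patients would then rest on a decision that the readable text does not describe, in a trial whose Phase I primary objective is to find the optimal doses.

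**Working it through.** **1. The plan's own figure.** Inputs from Section 10.1: null rate 18%, alternative 36%, one-sided alpha 0.10, n = 27. Exact binomial test, success if at least 8 respond:

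- P(X ≥ 8 | n = 27, p = 0.18) = 0.0977
- P(X ≥ 8 | n = 27, p = 0.36) = 0.812

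The stated 80% power is reproduced. Adding 10% gives 27 × 1.10 = 29.7, rounded to 30, the cohort size in Section 5.3. This calculation does not involve the dose level, so the choice of level changes neither its error rate nor its power at the stated rates.

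**2. Order of the doses.** One level lies below another if neither drug is higher and at least one is lower.

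| Level | Carfilzomib, mg/m² | Panobinostat, mg |
|---|---|---|
| 4 | 20/45 | 30 |
| 5 | 20/56 | 30 |
| 6 | 20/56 | 20 |

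Level 4 is below Level 5 (45 < 56, equal panobinostat). Level 6 is below Level 5 (equal carfilzomib, 20 < 30). Levels 4 and 6 are unordered (45 < 56 but 30 > 20), the only such pair among Levels 1 to 6. Levels -1 to 5 are fully ordered.

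**3. The rules read by dose.** The step-back rule speaks of a lower dose and the MTD definition of the highest dose level, so dose is the natural reading. Levels 1 to 4 are taken as passed, since Section 5 reports no DLTs.

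| Level 5 | Level 6 | Highest passing level |
|---|---|---|
| cleared | not opened | 5 |
| cleared | cleared | 5 |
| cleared | exceeded | 5 |
| exceeded | not opened | 4 |
| exceeded | exceeded | 4 |
| exceeded | cleared | 4 and 6 unranked |

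Five of six outcomes give one level. In the third row, stepping back from Level 6 alone would lead to Level 3 (20/45 mg/m², 20 mg), because Level 4 is unranked against it. Level 5 is still the highest passing level, and that row needs the smaller combination to be the more toxic one.

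If Level 5 is tested first, the last row arises only by sponsor assignment, since no written rule opens Level 6 after Level 5 is exceeded. The missing rank has no consequence for expansion there. Section 5 already fixes Phase II at Level 4, the expansion trigger is tolerability rather than the MTD label, and Level 6 is then the only tolerable added level.

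**4. The expansion choice.** Level 4 plus one added cohort: 30 + 30 = 60, as Section 5.3 states. Level 4 plus two: 30 + 30 + 30 = 90, above 80. So at most one added level can be fully expanded, and a choice is needed only if both are tolerable. For an assumed DLT rate p, a 3+3 cohort passes with probability (1−p)³ + 3p(1−p)² × (1−p)³. With equal rates and independent cohorts:

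| Assumed DLT rate | One level passes | Both pass |
|---|---|---|
| 10% | 0.91 | 0.82 |
| 20% | 0.71 | 0.50 |
| 30% | 0.49 | 0.24 |

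The choice is therefore a realistic one. Its size is one cohort of 30, or at most 30 + 6 = 36 patients at the chosen level.

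**The case for a change.** The best case for a change runs as follows. The enrollment confirmation tells a site which level was assigned, not why. Level 5 entered with Amendment 3 (March 2013) and Level 6 with Amendment 4 (October 2013), which suggests a sequence but gives no decision rule. Both levels may well prove tolerable, so the sponsor could choose after seeing data. The section on enrolling at the MTD once it is determined does not settle the matter, because expansion turns on tolerability. One short decision table would close the gap without adding procedures.

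The facts in that case stand: the opening condition and the selection criterion are not written in any readable passage. The harm is much smaller than it first appears. Escalating to a smaller combination, or stepping back to a larger one, requires dose words to be read as label numbers, under rules that cite only Table 2. Each level is still judged on its own DLT count, and two or more DLTs still mean that the MTD is exceeded. The stated basis for expansion is tolerability, not response. If early responses did influence the choice, that level's Phase I patients would be at most 6 of 36. The proposed table would record a sponsor decision; it would not replace a faulty method with a better one.

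**Conclusion.** No change is needed. The dose comparison is correct, and the numbering in Table 3 does not follow dose order. What survives is a gap in detail: when Level 6 opens after Level 5 is exceeded, and which added level is expanded if both are tolerable. The sponsor, which assigns every patient's level centrally, can settle both in running the study. How Table 3's numbering is reconciled with Sections 5, 5.2.1, 5.2.3 and 5.3 is also for the sponsor; nothing here says which dose, level or sequence is right.

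The effect is confined to the parallel Phase I and one added cohort of 30 (at most 36 patients at that level). Phase II at Level 4, the response objective tied to the first four levels, and the sample size of 27 are unaffected.

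This rests on three assumptions: the rules are read by dose, Levels 1 to 4 count as passed, and expansion follows tolerability as Sections 5 and 5.3 state. Figure 2 could not be seen. If it shows the sequence, the gap is smaller still.
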